Reach Out: Emergency Department-Initiated Hypertension Behavioral Intervention Connecting Multiple Health Systems

NCT03422718

9/1/2018

Reach Out
Statistical Analysis Plan
September 2018

1. Review of statistical design

Reach Out is a health system focused, multicomponent, multiphase optimization strategy (MOST), health theory based, mobile health behavioral intervention to reduce BP among hypertensive patients evaluated in a safety net ED. This trial will take place in Flint, Michigan, an urban, under-resourced, predominately African American community with which the researchers have long-standing partnerships. Reach Out consists of three components, each with two levels: 1) healthy behavior text messaging (yes vs. no), 2) prompted home BP self-monitoring (weekly vs. daily), and 3) facilitated primary care provider appointment scheduling and transportation (yes vs. no).

Table 1: Reach Out ED Intervention Arms			
Arm	Healthy Behavior Text	Prompted BP self-monitoring frequency	Facilitated Primary Care appointment scheduling and transportation
1	No	Low	No
2	Yes	Low	No
3	No	High	No
4	Yes	High	No
5	No	Low	Yes
6	Yes	Low	Yes
7	No	High	Yes
8	Yes	High	Yes

Subjects will be block randomized into one of the eight experimental arms (Table 1) and followed for 12 months. Importantly, the intervention components may have important associations with subjects' baseline characteristics. We are most interested in three baseline characteristics: age, sex, and antihypertensive use. Thus, to ensure scientific rigor, in randomization we will reduce imbalance within our treatment arms by stratifying randomization with these variables: 1) age (<64, ≥ 65); 2) sex, as reported by participant; 3) taking an antihypertensive within the last 6 months (yes vs. no).

Our overarching objective is to demonstrate that an ED initiated, multicomponent, health system intervention can meaningfully reduce BP in a traditionally underserved population.

Primary Objective: Estimate the expected change in 12-month SBP reduction associated with each level of the three interventions and determine the combination of elements that appears most promising for study in a future larger scale trial.

Primary Endpoint: The primary endpoint is the change in systolic BP from baseline to 12 months.

Secondary Endpoints: Time from ED visit to arrival at first primary care visit (in days); Attendance at two or more primary care visits within 12 months of randomization

Sample Size: We plan to enroll approximately 960 patients into the eligibility phase. From this group, we estimate that 480 subjects will report qualifying BPs and will be randomized to one of the eight intervention arms. We anticipate 240 subjects will fully complete the 12 month, in person follow up visit. For 80% power to detect the smallest main expected effect of 0.35 based on the Collins method of a 3-factor experiment analyzed using a second order model (i.e. main effects and 2-way interactions), we require 196 subjects. Assuming 480 randomized subjects and allowing an additional 50% loss to follow up after the eligibility phase, we expect at

least 240 subjects, exceeding 80% power with an alpha level of 0.10 (inflated to reduce likelihood of dismissing active components with modest BP reducing effect) – we used the FactorialPowerPlan SAS macro to calculate power. For the secondary analyses, considering an alpha of 0.05 and a baseline proportion attending 2 or more primary care provider visits within one year of 40%, with a total sample size of 240 evenly distributed between the active appointment scheduling and passive appointment, we have 87% power to detect an increase to 60% attending 2 or more visits. The time to event analysis (considering an alpha of 0.05, power of 99%, and 240 subjects enrolled over 720 days, followed for 30 days) can detect a change from 20% of subjects in the non-facilitated group to 20.4% of subjects in the facilitated group.

Analysis Plan: The primary analysis (aim 1) will fit a linear regression model with the outcome of SBP change (baseline minus 12 months) and main effect-coded binary predictors of healthy behavior texts (yes vs. no), prompted BP self-monitoring frequency (high vs. low), and primary care provider visit scheduling and transportation (active vs. passive). Initial analyses will focus on the main effects. Additional analyses will include all the two-way interactions of the three intervention components (only considering interactions where at least one of the factors in the interaction demonstrates a sufficiently large main effect). As the goal of this exploratory trial is to find interventions and combinations with activity, we will use an alpha level of 0.10 for all main effects and 0.20 for interactions. We plan to include elements meeting that bar for statistical significance in the subsequent multicenter trial. If significant interactions exist (i.e. the combination of facilitated transportation and high frequency home BP monitoring), we plan to implement the combination of elements that has the highest expected reduction in SBP – assuming we achieve significance at the p=0.1 (main effects) or 0.2 (interaction) level for the components. In the event of an overall “null” trial, we would examine the expected change in SBP for arm 1, which would be represented by the intercept. If this was significantly greater than 0 at the p=0.1 level we would propose a very simple subsequent multi-center trial using only weekly prompted BP self-monitoring.

The main secondary analyses (aim 2) will use time-to event (Cox Proportional Hazards) and logistic regression. For the endpoint of interest, (either time to first primary care visit, or the binary variable indicating attendance at two or more primary care visits within 1 year of randomization), we will fit an adjusted regression model. The main predictor of interest for these models is assignment to the active primary care provider scheduling and transportation arm (50% of all subjects randomized in the trial), while adjusting for the assignment into other groups similar to aim 1 (healthy behavior text messages and prompted BP self-monitoring).

2. Analysis Plan

2.1 Preliminary evaluation of data:

Purpose: To identify issues that will affect our approach to the primary analysis. Specifically:

to summarize the amount of missing data for key variables and to examine the distributional characteristics of key variables in order to detect potential data entry/reduction errors

Methods: All intervention groups will be combined. Any variable that requires creation from collected data will be coded and created for examination. Continuous variables will be summarized by minimum, maximum,

arithmetic mean, median, and standard deviation. Histograms and boxplots will be used to assess distributional characteristics of baseline and follow-up variables. The change in systolic BP from baseline to 12 months will be summarized and plotted to assess distributional characteristics. Categorical variables will be tabulated with frequencies and percentages. The number and percentage of missing observations for all variables will be reported for each variable for the entire sample. Missingness for the primary and secondary outcome variables will be assessed by intervention group to evaluate any differential missingness.

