3 CONTEMPORARY CONTROL GROUP

To better understand how the intervention will or has affected Reach Out participants, we will retrospectively create a contemporary control group. This control group will encompass HMC ED patients who had follow-up visit (outpatient or ED) within 12 months of their ED visit. Patients will be identified through review of the HMC EMR, during a similar period to when the Reach Out intervention was being conducted (March 2019-August 2020). If not possible to make adequate comparisons during the trial time period, it may be expanded. All data will be outgoing from HMC to the study team. We request a waiver of HIPAA authorization and waiver of consent. We will exclude all patients that were consented into the study, the contemporary control group will be de-identified following participant exclusion. We will collect the minimum amount of personal data possible to accomplish the comparison including similar variables to:

- Stratifying variables (sex, age, antihypertensive use)
- Demographics (race, ethnicity)
- Date of ED visit
- ED complaint
- ED BPs
- Date of follow-up
- BPs at follow-up
- Time to follow-up

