We will conduct additional exploratory analyses using the stratification factors (age, sex, and antihypertensive use) as covariates. As uncertainty exists on the distribution of enrolled participants within these strata (e.g. young men taking antihypertensive medication), we cannot estimate the preliminary statistical power for these exploratory aims. Thus, we will estimate the power based on the strata sizes prior to conducting the exploratory analyses. Interaction terms (e.g. age with behavioral interventions, sex with behavioral interventions, etc.) will be utilized to determine if specific groups respond well to specific intervention elements. Baseline BP may also play an important role. We will examine its impact by dividing the cohort into tertiles. We will repeat the above primary and exploratory modeling within each of the three initial BP strata to determine if there is heterogeneity of effect (e.g. do patients with the highest baseline BPs get the most benefit from the intervention components?). We will similarly assess the impact of the intervention components on the exploratory and process outcomes using linear, Poisson, logistic, or ordinal regression depending on the distributions. In addition, we will conduct longitudinal analyses that include all BP measurements over time (including those by text and at the in-person visits) to assess the temporal profiles of response in the intervention components.

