2.4. Primary analysis/results

Purpose: Primary results for the intention to treat (ITT) analysis.

Methods/Approach:

Intention to Treat Dataset: all subjects randomized into study and all data observed from each subject regardless of compliance and adherence with the assigned intervention or follow-up.

Primary outcome: Change in systolic BP from baseline (median of three qualifying SBP from eligibility phase) to 12 months. Baseline minus 12 months.

Primary analysis: The primary analysis will fit a linear regression model with the outcome of SBP change and main effect-coded binary predictors of healthy behavior texts (yes vs. no), prompted BP self-monitoring frequency (high vs. low), and primary care provider visit scheduling and transportation (active vs. passive) and the stratification variables. Initial analyses will focus on the main effects. The outcome will be transformed (e.g., log) if necessary.

$$(BL\ BP - 12\ mo\ BP) = \beta_0 + \beta_1\ HBtexts + \beta_2\ HighBPmonitor + \beta_3\ PCPfacilitated + \beta_4\ female + \beta_5\ Age > 65 + \beta_6\ AHT + \beta_7\ Black$$

Where HBtexts= 1 for daily healthy behavior texts and 0 for none; HighBPmonitor=1 if daily BP monitoring and 0 for weekly; PCPfacilitated=1 for provider scheduling and transportation facilitated and 0 for not facilitated; female = 1 for self-reported female, 0 for male; Age>65=1 for Age \geq 65, 0 for 18-64; and AHT=1 for antihypertensives in the past 6 months, 0 for not; Black=1 for Black, 0 for Other

Missing data:

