We will work to prevent missing data by the recruitment and retention strategies described elsewhere. The amount and patterns of missing data and its associations with other variables (in particular intervention category) will be explored so that an appropriate statistical method for analysis can be used. If the data is missing at random (missing outcomes can be predicted from other observed variables, especially recent self-reported blood pressures), which we believe to be the most likely, since we obtain text messaging-based BPs at least weekly, the repeated measurements within individuals will allow us to use multiple imputation to handle sporadic missing at random BP measurements. For multiple imputation, we will use R package mice to impute the data using multiple imputation by chained equations. Non-normal continuous missing variables will be transformed for normality and back-transformed for any calculations necessary (e.g., change in BP). The imputation model will include all variables in the analysis model, treatment interactions, as well as other covariates that predict the missing variable and whether the missing variable is missing. Thus, associations between baseline variables and missing variables will be assessed both for strength of association and functional form. We will use 100*fraction of incomplete cases number of imputations. Analyses will combine regression estimates using Rubin's rules. Model checking will be performed on each imputed dataset through residual analysis to identify any issues with the imputation model or analysis model. Problems occurring in a small number of imputed datasets suggest a problem with the imputation dataset and problems occurring consistently across all imputed datasets suggest a problem with the analysis model.

In the case of non-ignorable missing (missing not at random) data, sensitivity analyses will be performed using pattern mixture or selection models to evaluate the robustness of our conclusions to a range of sensible conditions (for both the primary and additional analyses of the primary endpoint).

Interpretation:

Results will be reported as parameter estimates, 95% confidence intervals, and 2-sided p-values. As the goal of this exploratory trial is to find interventions and combinations with activity, we will use an alpha level of 0.10 for all main effects. Plots of mean BP levels over time will be generated for the 3 main effects and each intervention group.

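### The null-trial fallback rule equates arm 1 with the intercept, which is not so in the SAP 2.4 model, and its test against 0 is an uncontrolled before-after comparison

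*SAP*

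**What the plan says.** The rule stands in identical words in SAP section 1 (Analysis Plan) and protocol 9.1. In an overall null trial, "we would examine the expected change in SBP for arm 1, which would be represented by the intercept". Then: "If this was significantly greater than 0 at the p=0.1 level we would propose a very simple subsequent multi-center trial", using weekly prompted self-monitoring only. Neither document says which fitted model supplies the intercept. The paragraph that contains the rule describes a model with "main effect-coded binary predictors of healthy behavior texts" and the two other components, and no covariates.

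SAP 2.4 writes out the primary model as an equation. It codes the components 0/1 and adds four 0/1 terms, none of them centred: female, age 65 or over, antihypertensive use in the past 6 months, and race ("Black=1 for Black, 0 for Other"). The protocol keeps covariates out of its primary model: "We will conduct additional exploratory analyses using the stratification factors (age, sex, and antihypertensive use) as covariates".

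SAP 2.4 defines the outcome as "Change in systolic BP from baseline (median of three qualifying SBP from eligibility phase) to 12 months", computed as baseline minus 12 months, so a positive value is a fall. Protocol 5.3.4 randomizes participants who text at least one reading with SBP of 140 or more or DBP of 90 or more during that same phase. Protocol 6.1 makes arm 1 the effective control and states that there is no untreated group. On sidedness, SAP 2.4 says: "Results will be reported as parameter estimates, 95% confidence intervals, and 2-sided p-values". The rule itself does not state its sidedness.

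**The concern.** The rule is a go/no-go decision for a multicentre trial, and it raises two separate questions.

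The first is what is tested. An analyst who fits the primary model as SAP 2.4 writes it, and reads off the intercept, gets the arm-1 value for non-Black men aged 18-64 not on antihypertensives. That is not arm 1's mean.

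The second is what the test means. Even with the right quantity, a change from baseline in one arm, tested against 0, does not isolate the effect of weekly prompting. Participants enter because an eligibility-phase reading was high, and baseline comes from that phase. Part of any fall can be regression to the mean, and no randomized arm shows how much.

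**Working it through.** The rule has no sample size, power or expected value of its own to reproduce. One related figure bears on sidedness. The plan's 196 for a main effect reproduces with an effect of 1/2.8 = 0.357, 80% power and two-sided alpha 0.10 (noncentral t: 196). One-sided alpha 0.10 gives 142 (normal approximation). I therefore read the plan's alpha as two-sided, so the nominal chance of a false positive in the favourable direction is 5%.

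**Intercept against arm-1 mean, SAP 2.4 model.** With all component indicators at 0,

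arm-1 mean = β0 + β4·P(female) + β5·P(age ≥65) + β6·P(AHT) + β7·P(Black),

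so the intercept misses the mean by the prevalence-weighted covariate coefficients. The documents give no coefficients. As an illustration only, each 1 mm Hg of race coefficient moves the intercept by 0.57 mm Hg if 57% are Black. That is the protocol's figure for Flint, not for the trial sample.

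**Precision.** For a balanced design with mutually independent covariates and the same residual SD s in both models:

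- Components only, 0/1: Var(β0) = 4·s²/N.
- SAP 2.4 model: Var(β0) = (4 + Σ p/(1−p))·s²/N.
- Assumed prevalences 57% Black, 50% female, 15% aged 65 or over, 50% on antihypertensives: 4 + 0.57/0.43 + 0.5/0.5 + 0.15/0.85 + 0.5/0.5 = 4 + 1.33 + 1 + 0.18 + 1 = 7.50.
- SE ratio: √(7.50/4) = 1.37.
- Over 40-60% female, 10-25% aged 65 or over and 30-70% on antihypertensives, with 57% Black held fixed: √(6.53/4) = 1.28 to √(9.49/4) = 1.54.
- Arm-1 mean averaged over the observed covariates: 4.00·s²/N, so no loss against the components-only model.

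**Test against 0 when nothing works.** The entry rule (SBP ≥140 or DBP ≥90), the median-of-three baseline and 240 completers come from the documents. The rest is assumed:

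- Usual SBP: mean 140-150, between-person SD 12-15, within-person SD 8-12.
- Usual DBP: mean 85-95, SD 10, within-person SD 0.6 times that of SBP.
- SBP-DBP correlation: 0.6 between persons, 0.5 within.
- Follow-up is one later reading with no true change.

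Simulated over these settings, the regression-to-the-mean fall is about 0.1-0.8 mm Hg, with a middle setting near 0.34.

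The firing rate is Φ(fall/SE − 1.645), with SE = SD(change)·√(4/240) = 0.129·SD(change). The median of three normal readings has variance about 0.449 times that of one reading, so SD(change) ≈ within-person SD × √1.449.

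- Middle: within-person SD 10, SD(change) 12.0, SE 1.55. Φ(0.34/1.55 − 1.645) = Φ(−1.43) = 7.7%.
- Low: fall 0.15, within-person SD 8, SD(change) 9.6, SE 1.24. Φ(0.12 − 1.645) = 6.4%.
- High: fall 0.80, within-person SD 12, SD(change) 14.4, SE 1.86. Φ(0.43 − 1.645) = 11.2%.

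So the rule fires in about 6-11% of such trials against 5%. Read as one-sided 0.10, it fires in about 12-20% against 10%.

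Protocol 5.3.4 allows randomization after a single texted reading, and one reading regresses more than a median of three. If 10%, 25% or 50% of participants had only one reading (assumed; the documents give no share), the rates become 7-16%, 8-24% and 11-41%.

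**The case against.** The best defence is that the rule closes a paragraph describing one model, with three components and no covariates, so the intercept is naturally that model's. Under 0/1 coding it is then arm 1's expected change. This stands for that model. It does not settle the matter, because SAP 2.4 also calls its model the primary analysis, is the only place with an equation, and has a different intercept.

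It is also fair that the trial calls itself exploratory, that the protocol openly gives its reason for having no untreated arm, and that the rule only proposes another trial. This limits the severity. A lenient alpha tolerates more chance error, but it does not supply a comparator.

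Four stronger readings are tempting, and the documents do not support them:

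- *The components are coded −1/+1, so the intercept is the mean of all eight arms.* The rule says that the intercept represents arm 1, which contradicts that coding, and the only coding the SAP writes out is 0/1.
- *The false-positive rate reaches 16% even with a median-of-three baseline.* That needs entry on SBP alone; the protocol admits on SBP or DBP.
- *Arm 1 must show a fall even if prompting does nothing.* Regression to the mean pushes that way. But baseline is home-measured and texted, while follow-up is in person or by tele-outcome (protocol 7.1.1 and 7.1.2), so the net change also depends on the difference between methods.
- *The external group supplies the comparator.* Protocol section 3 says "we will retrospectively create a contemporary control group", but does not tie it to this rule. It states no BP threshold for that group, whereas participants needed an ED SBP of at least 160 or DBP of at least 100, and its follow-up is any visit within 12 months. Setting the two changes side by side would add selection bias.

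**Conclusion.** The point holds and is minor. Applied to the SAP 2.4 model, the rule tests one covariate profile instead of arm 1's mean, with a standard error about 37% larger (28-54%) at assumed prevalences. The size of the gap in mm Hg cannot be stated. A reader might put it at 1.7 mm Hg by giving all four covariates a 1 mm Hg coefficient of the same sign (0.57 + 0.50 + 0.15 + 0.50 = 1.72), but nothing in the documents supports those coefficients.

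Under any model the test is an uncontrolled before-after test. That conclusion rests on the documents alone. The size of the regression-to-the-mean push and the resulting firing rates rest on the assumed BP distributions. With a median-of-three baseline the inflation is modest; it grows if many participants contribute a single reading.

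The rule operates only after a null result. The main-effect estimates and tests are unaffected.

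**What to change.** Two changes in each document:

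1. In SAP section 1, replace the clause that identifies arm 1's change with the intercept by: *which would be the arm-1 adjusted (marginal) mean on the mm Hg scale from the Section 2.4 model, averaged over the observed sex, age group, antihypertensive use and race*. In protocol 9.1, refer to the same SAP quantity. Stating the mm Hg scale matters because SAP 2.4 allows the outcome to be transformed.
2. In both, replace the sentence that makes significance above 0 the trigger by: *This is an uncontrolled before-after change; it will be reported with its 95% confidence interval as descriptive, and exceeding 0 will not by itself be taken as evidence that weekly prompting lowers SBP or as sufficient to propose a trial.*

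No new data are needed, and the adjusted mean loses no precision against the components-only intercept. The cost is that the fallback proposal becomes harder to reach: the automatic trigger goes, and a trial of weekly prompting alone would need further justification.

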2.2. Description of study process

Purpose: To compare how the study unfolded with the pre-trial plan to determine if changes in the pre-trial analysis plans are warranted.

Methods/Approach:

- CONSORT flow figure
- Number screened; number enrolled
- Subjects randomized (number to each group)
- Retention by group
- Final completion rates
- Number of subjects in analysis data sets

2.3. Description of participants

Purpose: To describe the patient population by intervention group.

Methods/Approach: Construct “table 1” describing the baseline characteristics of each intervention group including:

- Demographic characteristics
- Baseline medical history, Tobacco/Alcohol Information, Insurance Status, Transportation Status, Social Cognitive Theory Measures, medication history, medication adherence
- Baseline values of primary and/or secondary outcome variables: BP, PCP Attendance

Means and standard deviations will describe continuous variables, frequencies and counts will describe categorical variables. Significance testing of baseline differences between groups will not be performed based on statistical and CONSORT recommendations.¹⁻²

Intervention Exposure: Participants receiving daily BP monitoring or healthy behavior text messaging can choose to “snooze” (stop texts for 2 weeks) or de-escalate their treatment “weekly” (stop healthy behavior text messages, move to weekly BP monitoring). Participants with weekly BP monitoring can choose to “snooze” treatment (stop texts for 2 weeks) or escalate their treatment “daily” (daily BP monitoring no change to healthy behavior text messaging). The number and percentage of participants who “snooze” BP monitoring and healthy behavior texts, both daily and weekly, will be reported separately. The number and percentage of participants who choose to de-escalate from daily BP monitoring and healthy behavior texts will be reported separately as well the number and percentage who escalate their treatment. The proportion of all possible BP monitoring texts (either daily or weekly) completed for each subject will be calculated and the proportion and 95% confidence interval will be reported by intervention group.

